**Combination (Part 2D)h:**

MSS CRC: progressed or relapsed at least 1 prior standard therapy No prior anti-CTLA4 allowed.

BMS-986218 dose TBD + Nivolumab TBDi mg, Q4W (n=40)

- a If Part 1 is open upon the decision to initiate Part 2, treatment in the 2 parts will occur in parallel. If supported by clinical and safety data, doses higher than 200 mg may be studied until MTD is reached, and further details will be provided in a subsequent protocol amendment at such time.
- b If Part 1 is open upon the decision to initiate Part 2, treatment in the 2 parts will occur in parallel. If supported by clinical and safety data, doses higher than 100 mg may be studied until MTD equivalent is reached in participants, and further details will be provided in a subsequent protocol amendment at such time.
- c If Part 1B is open upon the decision to initiate Part 2C and Part 2D, treatment in the 2 parts will occur in parallel. If supported by clinical and safety data, doses higher than 200 mg BMS-986218 may be studied until MTD is reached, and further details will be provided in a subsequent protocol amendment at such time.
- d Tumor-specific eligibility criteria are detailed in [Section 6](#).
- e Additional participants may be treated or randomized to further evaluate emerging data or subgroups of interest if needed but not to exceed 40 participants per dose level in Part 2A and Part 2B.
- f Participants will be randomized, which will include ipilimumab monotherapy and BMS-986218 at different dose levels.
- g Participants will be treated or randomized.
- h Dose(s) of BMS-986218 selected for Part 2C and Part 2D will be based on the totality of preliminary safety, tolerability, efficacy, PK and PD data.
- i The nivolumab dose found to be tolerable in Part1B will be used in Part 2 combination expansions (Part 2C and Part 2D)

Abbreviations: CTLA = cytotoxic T-lymphocyte-associated protein 4; DLT = dose-limiting toxicity; mCRPC = metastatic castration-resistant prostate cancer; MSS CRC = microsatellite stable colorectal cancer; MTD = maximum tolerated dose; NSCLC = non-small cell lung cancer ; PD = pharmacodynamic; PD-L1 = programmed death-ligand 1; Q2W = every 2 weeks; Q3W = every 3 weeks; Q4W = every 4 weeks; R = randomized; SCCHN = squamous cell carcinoma of the head and neck; TNBC = triple-negative breast cancer.

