**Combination (Part 2D)b:**

MSS CRC: progressed or relapsed at least 1 prior standard therapy No prior anti-CTLA4 allowed.

[figure not shown]
BMS-986218 dose TBD + Nivolumab TBD i mg, Q4W (n=40)

- a If Part 1 is open upon the decision to initiate Part 2, treatment in the 2 parts will occur in parallel. If supported by clinical and safety data, doses higher than 200 mg may be studied until MTD is reached, and further details will be provided in a subsequent protocol amendment at such time.
- b If Part 1 is open upon the decision to initiate Part 2, treatment in the 2 parts will occur in parallel. If supported by clinical and safety data, doses higher than 100 mg may be studied until MTD equivalent is reached in participants, and further details will be provided in a subsequent protocol amendment at such time.
- c If Part 1B is open upon the decision to initiate Part 2C and Part 2D, treatment in the 2 parts will occur in parallel. If supported by clinical and safety data, doses higher than 200 mg BMS-986218 may be studied until MTD is reached, and further details will be provided in a subsequent protocol amendment at such time.
- d Tumor-specific eligibility criteria are detailed in [Section 6](#).
- e Additional participants may be treated or randomized to further evaluate emerging data or subgroups of interest if needed but not to exceed 40 participants per dose level in Part 2A and Part 2B.
- f Participants will be treated or randomized, which will include ipilimumab monotherapy and BMS-986218 at different dose levels.
- g Participants will be treated or randomized.
- h Dose(s) of BMS-986218 selected for Part 2C and Part 2D will be based on the totality of preliminary safety, tolerability, efficacy, PK and PD data. Refer to [Section 5.1.2.4](#) for additional details.
- i The nivolumab dose found to be tolerable in Part1B will be used in Part 2 combination expansions (Part 2C and Part 2D)

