#### **5.2 Number of Participants**

The approximate total number of evaluable participants will be up to 684 as shown below:

- Part 1 - Dose Escalation Phase: Up to approximately 284 evaluable participants may be treated in the escalation phase including:
  - Part 1A - up to approximately 200 evaluable participants for the BMS-986218 Monotherapy Escalation
    - Part 1A Q4W monotherapy - up to approximately 108 DLT-evaluable participants will be treated.
    - Part 1A Q2W monotherapy - up to approximately 72 DLT-evaluable participants will be treated.

- Part 1A PD cohort - approximately 20 evaluable participants will be treated in the Part 1 PD cohorts.
  - In addition, in order to evaluate more than one dose level or schedule, up to 40 additional evaluable participants may be treated in the Part 1A PD cohorts (from participants initially planned for other Part 1 cohorts), provided the total number of participants in Part 1 is not exceeded.
- Part 1B - up to approximately 84 DLT-evaluable participants for the Safety Evaluation of Combination Doses of BMS-986218 with Nivolumab.
- Part 2 - Dose Expansion Phase: The remaining 400 response-evaluable participants represent the potential number of participants in BMS-986218 cohort expansions who may be either randomized (Part 2A and Part 2B) or treated (Part 2C and Part 2D) including:
  - Part 2A - for the Randomized BMS-986218 Monotherapy Cohort Expansion in Cutaneous Melanoma, approximately 132 evaluable participants will be randomized, with 33 evaluable participants per arm required.
  - Part 2B - for the BMS-986218 Monotherapy Cohort Expansion in NSCLC, approximately 66 evaluable participants will be randomized, with 22 evaluable participants per arm required.
  - In Part 2A and Part 2B, additional participants may be treated or randomized to further evaluate emerging data or subgroups of interest if needed but not to exceed a total of 40 evaluable participants per arm. If additional participants are treated or randomized in Part 2A and Part 2B, then up to 160 response-evaluable participants (= 40 participants  $\times$  4 arms) and 120 response-evaluable participants (= 40 participants  $\times$  3 arms) can be randomized in Part 2A and Part 2B, respectively.

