### 7.4 Method of Treatment Assignment

During the screening visit, the investigative site will call into the enrollment option of the IRT designated by BMS for assignment of a 5-digit participant number that will be unique across all sites. Enrolled participants, including those not dosed, will be assigned sequential participant numbers [REDACTED]. The patient identification number

(PID) will ultimately be comprised of the site number and participant number. For example, the first participant screened (ie, enrolled) at site number 1, will have a PID of [REDACTED]. Once it is determined that the participant meets the eligibility criteria following the screening visit, the investigative site will call the IRT to centrally assign the participant into the open dose panel. If Part 1 is open upon the decision to initiate Part 2, treatment in the 2 parts will occur in parallel.

In the Randomized BMS-986218 Monotherapy Cohort Expansion in Cutaneous Melanoma (Part 2A), all participants will be centrally randomized evenly across study arms, which will include: BMS-986218 monotherapy at 7 mg, 20 mg, 70 mg Q4W or ipilimumab 3 mg/kg Q3W (maximum of 4 doses).

In the Randomized BMS-986218 Monotherapy Cohort Expansion (Part 2B), participants will be randomized evenly across study arms, which will include: BMS-986218 at 7 mg, 20 mg, and 70 mg Q4W.

In Part 2A and Part 2B, if it is decided based on a preliminary assessment of anti-tumor activity that not all arms would need to continue enrollment, randomization would continue only in the arm(s) that remain open. In addition, more subjects may be enrolled in selected arm(s) as specified in [Section 5.2](#) to better assess an initial signal.

In Part 2C Combination Expansion, multiple doses may be open concurrently. In that case, treatment assignments will alternate between the dose levels, with consecutively treated participants assigned to different parts through IRT whenever possible. If there are no openings available in the dose level to which the participant would be assigned by this algorithm, then the subject will be assigned to the next open dose.

In Part 2D Combination Expansion, participants will be assigned to one dose.

In Part 2, BMS-986218 Q4W will be administered for a maximum duration of 2 calendar years, and ipilimumab Q3W will be administered for a maximum of 4 doses.

For Part 2, participant replacement will not be allowed for participants who are discontinued after dosing.

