#### **10.1.3    *The Randomized BMS-986218 Monotherapy Cohort Expansion in Cutaneous Melanoma (Part 2A)***

The primary purpose of the Randomized BMS-986218 Monotherapy Cohort Expansion in Cutaneous Melanoma (Part 2A) is to evaluate preliminary efficacy of BMS-986218 relative to ipilimumab 3 mg/kg. One hundred and thirty two response-evaluable participants will be randomized to BMS-986218 or ipilimumab evenly across study arms (eg, 33 participants to BMS-986218 at 7 mg Q4W; 33 participants to BMS-986218 at 20 mg Q4W; 33 participants to BMS-986218 at 70 mg Q4W; and 33 participants to ipilimumab) and stratified by the outcome (ie, progressed, relapsed) of previous anti-PD-1/PD-L1 immunotherapy. Additional response-evaluable participants may be randomized to further evaluate emerging data or subgroups of interest if needed but not to exceed 40 response-evaluable participants per arm. If additional participants are randomized, up to 160 response-evaluable participants (= 40 participants  $\times$  4 arms) may be randomized in Part 2A. The ORR of ipilimumab will serve as a control. With 33 treated participants in each BMS-986218 arm, the lower limit of the 1-sided 80% confidence interval for ORR difference from ipilimumab arm will be 12%, 7.3%, or 2.7%, assuming effect size of 20%, 15%, or 10%, respectively.

Although the above assumptions on the response rate were used for the purpose of sample size calculation, it should be noted that, to date, there are no anti-tumor response data available in this post anti-PD-1/PD-L1 population. The efficacy evaluation criteria may evolve by the time when the tumor data from this study are matured for evaluation.

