**Table 10.3.1-1: Efficacy - Statistical Analyses**

Endpoint	Statistical Analysis Methods
ORR is defined as the proportion of all treated participants whose BOR is either CR or PR by Investigator per RECIST v1.1 or per PCWG 3 criteria for prostate.  BOR for a participant will be assessed per RECIST v1.1 by Investigator, unless otherwise specified.	Estimate of ORR and corresponding 2-sided exact 95% CI using the Clopper-Pearson method by treatment for each tumor type.  For part 2A, estimate of difference in ORR between arms (using ipilimumab as reference) and corresponding 2-sided exact 95% CI using the Clopper-Pearson method by BMS treatment arms.
Median DOR  DOR for a participant with a BOR of CR or PR is defined as the time between the date of first response and the date of the first objectively documented tumor progression per RECIST v1.1 or per PCWG 3 criteria for prostate, or death, whichever occurs first.	Estimate by the Kaplan-Meier method and corresponding 2-sided 95% CI using Brookmeyer and Crowley methodology (using log-log transformation) by treatment for each tumor type.
PFSR at 24, 36, and 48 weeks  PFS for a participant is defined as the time from the first dosing date to the date of first objectively documented disease progression or death due to any cause, whichever occurs first.	Estimate PFSR by the Kaplan-Meier method and corresponding 2-sided 95% CI using Greenwood formula by treatment for each tumor type.  For part 2A, estimate difference in PFSR between arms (using ipilimumab as reference) by the Kaplan-Meier method and corresponding 2-sided 95% CI using Greenwood formula by BMS treatment arms.  Estimate median PFS by the Kaplan-Meier method and corresponding 2-sided 95% CI using Greenwood formula by treatment for each tumor type.

Abbreviations: BOR = best overall response; BMS = Bristol Myers Squibb; CI = confidence interval; CR = complete response; DOR = duration of response; ORR = objective response rate; PCWG 3 = Prostate Cancer Working Group; PFSR = progression-free survival rate; PR = partial response; RECIST = Response Evaluation Criteria in Solid Tumors.

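### Part 2A arms may close or be extended on observed activity, with nothing keeping ipilimumab open or limiting the ORR and PFSR differences to concurrently randomised participants

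*Combined protocol and SAP*

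**What the plan says.** **Closing and extending arms.** Section 7.4 starts Part 2A with central, even randomisation to three BMS-986218 doses and ipilimumab. It then sets a condition for stopping some of them: "if it is decided based on a preliminary assessment of anti-tumor activity that not all arms would need to continue enrollment". The stated consequence for allocation is that "randomization would continue only in the arm(s) that remain open". It adds that "more subjects may be enrolled in selected arm(s) as specified in" Section 5.2. Section 10.3.9 allows a cohort to close on an inadequate signal. Neither section gives a timing, a threshold or a rule for the ipilimumab arm.

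**How added participants enter.** The texts disagree.
- Section 5.2: "additional participants may be treated or randomized to further evaluate emerging data or subgroups of interest if needed", up to 40 per arm. The Number of Participants part of the synopsis says the same.
- Footnote f of Figure 5.1-1: "Participants will be treated or randomized, which will include ipilimumab monotherapy and BMS-986218 at different dose levels".
- Footnote f of the synopsis figure (Figure 1-1): "Participants will be randomized, which will include ipilimumab monotherapy and BMS-986218 at different dose levels".
- Section 10.1.3: "Additional response-evaluable participants may be randomized to further evaluate emerging data or subgroups of interest".

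**Analysis.** Section 10.3.1 places the final primary efficacy analysis of Part 2A on the randomised population and allows a supplemental all-treated analysis. Table 10.2-1 defines the randomised population as everyone randomised in Parts 2A or 2B, whatever the date. For Part 2A, Table 10.3.1-1 asks for an "estimate of difference in ORR between arms (using ipilimumab as reference"), and for the PFSR difference on the same reference. The same table defines ORR as a proportion of all treated participants.

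**The concern.** Efficacy relative to ipilimumab is a primary objective, and Part 2A is the only part with that control. Randomisation protects the comparison only for people who could have been allocated to either arm. If ipilimumab stops while a BMS-986218 arm goes on, the later entrants are compared with earlier controls.

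The protocol's own rules make a change in case mix plausible. Section 5.2 lets additions target subgroups of interest. Section 6.1 caps at 70% the randomised participants who progressed within 6 months of starting anti-PD-1/PD-L1 therapy, so the mix can change once the cap is reached. The trial is open label with Investigator-reported response (Section 5.4.8). Nothing in Table 10.3.1-1 adjusts for enrolment period.

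**Working it through.** **Inputs from the documents.** 33 per arm planned and 40 per arm maximum (Sections 5.2 and 10.1.3); lower limits of the 1-sided 80% confidence interval for the ORR difference of 12%, 7.3% and 2.7% at true differences of 20, 15 and 10 points (Section 10.1.3).

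**Assumptions.** Ipilimumab ORR of 10% (not stated, back-solved in step 1); drift in ORR between early and late entrants of 5 to 10 points; for the second case only, ipilimumab closing at 20.

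**1. The plan's own figure.** Limit = d − 0.8416 × √[pₜ(1−pₜ)/nₜ + p_c(1−p_c)/n_c], with pₜ = p_c + d. With p_c = 10% and 33 per arm:
- d = 20: 0.20 − 0.8416 × √(0.21/33 + 0.09/33) = 12.0%
- d = 15: 0.15 − 0.8416 × √(0.1875/33 + 0.09/33) = 7.3%
- d = 10: 0.10 − 0.8416 × √(0.16/33 + 0.09/33) = 2.7%

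These match. Solving each stated limit for p_c gives 9.8% to 9.9%. The stated precision therefore presumes 33 against 33 with an intact comparison.

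**2. Non-concurrent share and bias.** If a share s of an arm enters after ipilimumab closes and their ORR is shifted by δ, the difference is biased by s × δ, in the direction of the drift.
- Case A, ipilimumab stops at 33 and one arm goes to 40: s = 7/40 = 17.5%; bias 0.175 × 5 = 0.9 to 0.175 × 10 = 1.75 points.
- Case B, ipilimumab stops at 20 and one arm goes to 40: s = 20/40 = 50%; bias 2.5 to 5 points.

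**3. Effect on the reading of the limit.** The chance that the 1-sided 80% lower limit exceeds zero when the drug equals ipilimumab (both 10%, exact enumeration, drift favouring the late entrants):
- 33 vs 33: 22.4%
- Case A: 22.5% without drift; 25.9% and 29.4% at 5 and 10 points
- Case B: 23.3% without drift; 31.4% and 40.4%

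**4. Precision under a concurrent-only comparison** (limits at d = 20/15/10, formula of step 1):
- Case A: everyone, 40 vs 33, 12.5/7.8/3.1%; concurrent only, 33 vs 33, 12.0/7.3/2.7%
- Case B: everyone, 40 vs 20, 11.7/6.9/2.2%; concurrent only, 20 vs 20, 9.7/5.1/0.6%
- Ipilimumab kept open to 40, 40 vs 40: 12.7/8.0/3.3%

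The PFSR difference has the same structure. It was not sized, because the plan gives no PFSR assumption.

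**The case against.** The strongest case on the other side is that Part 2A looks for a signal. Section 3.2.1 says no prospective hypothesis is formally evaluated, Section 10.1.3 speaks of preliminary efficacy, and Section 10.3.9 makes the interim looks descriptive. Dropping arms is deliberate flexibility, and Section 10.3 is a summary ahead of a SAP to be finalised before database lock. This stands as a limit on severity. It does not remove the gap: a later SAP can define a concurrent comparison, but it cannot supply controls who were never enrolled.

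Four stronger readings are tempting, and the documents do not support them.
- *Non-randomised additions enter the primary comparison.* Section 10.3.1 uses the randomised population, so participants who are only treated fall outside it. What remains is a wording conflict with the ORR definition in Table 10.3.1-1, and possible entry into the supplemental analysis. Sections 7.4 and 10.1.3 also point to randomisation.
- *The plan states that the whole ipilimumab arm is the reference.* Table 10.3.1-1 names ipilimumab only. That all of it is used follows from the population definition and the absence of any restriction.
- *Ipilimumab will close at 20.* No such look is set for Part 2A; the evaluation after about 20 belongs to Part 2C. Section 5.2 requires 33 evaluable participants per arm, although Section 7.4 does not rule out earlier closure.
- *Choosing the best-looking arm adds to this bias.* That is a separate problem. For three equal arms with true ORR 10%, picking the best at 20 overstates it by 5.7 points, and extension to 40 dilutes this to 2.9. Concurrent controls do not cure it.

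**Conclusion.** The point holds in a limited form. Followed as written, the plan can yield ORR and PFSR differences that are partly non-concurrent, and its statements on randomising added Part 2A participants contradict each other. In the case closest to the planned numbers, the bias is 0.9 to 1.75 ORR points; it becomes material, at 2.5 to 5 points, only if ipilimumab closes early. Both ranges rest on an assumed drift of 5 to 10 points, and the second also on an assumed closure at 20. With no formal test planned, a reader should not infer a breached alpha. The consequence is a biased estimate, and a lower limit that clears zero more often than the design figures suggest.

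**What to change.** 1. Reconcile Section 5.2, the synopsis and both footnotes f with Sections 7.4 and 10.1.3, so that every added Part 2A participant is randomised.
2. State that the primary ORR and PFSR differences use participants randomised while ipilimumab and the arm in question were both open. Report later or non-randomised participants descriptively.
3. Align the ORR denominator in Table 10.3.1-1 with the randomised population of Section 10.3.1 for Part 2A.
4. Preferably, keep ipilimumab open while any BMS-986218 arm enrols, within the 40-per-arm cap. This is optional.
5. Label any arm extended on observed activity as selected, since items 1 to 4 leave selection bias in place.

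Items 1 to 3 and 5 cost a few sentences. Item 2 lowers the confidence limits by about half a point in Case A and by 1.6 to 2.0 points in Case B. Item 4 costs up to 40 − 33 = 7 ipilimumab participants beyond the plan, or 40 − 20 = 20 more than if the arm had closed at 20. Both stay inside the cap of 160 (4 × 40).

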- In the BMS-986218 Combination Therapy Cohort Expansion (Part 2C) in NSCLC, the preliminary efficacy and safety of BMS-986218 in combination with nivolumab will be assessed in participants with NSCLC who have progressed or relapsed after anti-PD-1/PD-L1 therapy. Participants must not have received prior anti-CTLA-4 therapy in the advanced or metastatic setting. One or more doses to be evaluated in Part 2C will be selected from the range of doses assessed as tolerable in Part 1B, and which do not exceed the MTD or highest dose administered that has cleared safety. These dose(s) will be selected based on the totality of available safety, tolerability, efficacy, PK and PD data. The evaluation of efficacy in Part 2C will initially occur at one or more dose levels starting with up to 20 participants at each dose level. Additional participants up to 40 at a dose level may be evaluated following initial signal assessment. In Part 2C, participants will be treated Q4W for up to 2 calendar years regardless of treatment delays.
- In the BMS-986218 Combination Therapy Cohort Expansion in MSS CRC (Part 2D), the preliminary efficacy and safety of BMS-986218 in combination with nivolumab will be assessed in participants with MSS CRC who have progressed or relapsed on at least 1 prior standard therapy. Participants must not have received prior anti-CTLA-4 therapy in the advanced or metastatic setting. The dose to be evaluated in Part 2D will be selected from the range of doses assessed as tolerable in Part 1B, and which do not exceed the MTD or highest dose administered that has cleared safety. The dose will be selected based on the totality of available safety, tolerability, efficacy, PK, and PD data. Regardless of whether or not RAS mutation status is known, all participants will be tested during screening for extended RAS (NRAS and KRAS) and BRAF mutation status. Results from this testing at screening is not required prior to receiving treatment on study. The RAS status evaluation will be conducted with the goal of enrolling approximately 20 participants each with either mutation or wild-type with respect to extended RAS status. The Sponsor may elect to prioritize enrollment of participants based on mutation status. In Part 2D, participants will be treated Q4W for up to 2 calendar years regardless of treatment delays.

The duration of the study will be approximately 5 years.

The study design schematic is presented in Figure 5.1-1.

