## **7.5        Blinding**

This is an open-label study and randomized in Part 2. Designated personnel of the Sponsor will have access to treatment and/or randomization assignments prior to database lock to facilitate data analysis (see [Section 10.3.9](#)), as well as the bioanalytical analysis of PK and immunogenicity samples. A bioanalytical scientist in the Bioanalytical Sciences department of BMS Research & Development (or a designee in the external central bioanalytical laboratory) will have access to the randomized treatment assignments in order to minimize unnecessary bioanalytical analysis of samples.

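### Part 2C allocates concurrently open doses by predictable alternation in an open-label study; 1:1 randomisation through the same IRT would close a possible route to selection between doses

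*Combined protocol and SAP*

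**What the plan says.** Section 7.4 foresees that "In Part 2C Combination Expansion, multiple doses may be open concurrently". The allocation rule for this situation is that "treatment assignments will alternate between the dose levels, with consecutively treated participants assigned to different parts through IRT whenever possible". When the dose due next has no opening, "then the subject will be assigned to the next open dose", which is also a fixed rule. The section gives no reason for alternating and describes no way of concealing the next assignment.

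The sister cohorts are handled differently in the same section. In Part 2A, "all participants will be centrally randomized evenly across study arms". In Part 2B, a dose-only NSCLC cohort with no control arm, "participants will be randomized evenly across study arms, which will include: BMS-986218 at 7 mg, 20 mg, and 70 mg Q4W".

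Two sections disagree on the status of Part 2C. Section 7.5 says "This is an open-label study and randomized in Part 2", whereas Section 5.2 describes expansion participants as "either randomized (Part 2A and Part 2B) or treated (Part 2C and Part 2D").

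Part 2C starts with up to 20 participants per dose. Section 5.1 adds: "Additional participants up to 40 at a dose level may be evaluated following initial signal assessment". Section 10.1.5 bases the initial look on about the first 20 response-evaluable participants at a dose, with an 80% Clopper-Pearson interval. It notes that 3 responders are needed for that interval to exclude 5.5%. Section 5.4.8 bases response endpoints on investigator-reported best overall response. Section 6.1, criterion 2(k), lets the sponsor prioritise participants who had more than 6 months of disease control on prior anti-PD-1/PD-L1 treatment.

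**The concern.** Under alternation the next dose follows from the last one. In an open-label study the last dose is not hidden, and Section 7.5 gives designated sponsor personnel access to assignments before database lock. A person who can foresee the next dose can, deliberately or not, influence which patient takes that slot. Criterion 2(k) supplies a plausible prognostic basis for choosing. Some eligibility decisions also pass through the sponsor or medical monitor, such as agreement to a shorter washout in Section 6.2.

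What is at stake is whether the two dose groups are alike. If they are not, the response rates that will be read next to each other differ for reasons other than dose, and so does each dose's chance of showing the early signal that supports going from 20 to 40.

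**Working it through.** **1. The plan's own figures (Section 10.1.5).** Inputs: n = 40 per dose, null ORR 5.5%, alternative 15%, one-group chi-square test, one-sided alpha 0.10.

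Power = Φ{[(0.15 − 0.055) − 1.2816 × √(0.055 × 0.945/40)] / √(0.15 × 0.85/40)} = Φ{(0.0950 − 0.0462)/0.0565} = Φ(0.864) = 80.6%.

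The plan states about 80%, so the figure reproduces. The intervals at n = 20 also reproduce: 3/20 has a lower 80% limit of 5.64%, just above 5.5%, and 4/20 gives 9.0% to 36.1%. None of this depends on how participants are allocated between doses.

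**2. How predictable is the next assignment?** Suppose the last assignments are known and both doses have openings. For permuted blocks, the guesser names the dose used less often so far in the block and tosses a coin when they are equal. Every possible block was enumerated.

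| Method | Correct guesses |
|---|---|
| Alternation | 100% |
| Blocks of 2 | 75% |
| Blocks of 4 | 70.8% |
| Blocks of 6 | 68.3% |
| Simple randomisation | 50% |

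**3. What could steering do?** The documents give no rates for this, so every input here is an assumption. The two doses are truly equal. Half of the patients have a good prognosis. A share s of slots is filled with the preferred type, good for one dose and poor for the other.

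- Good-prognosis share, favoured dose: 0.5 + 0.5s. Other dose: 0.5 − 0.5s.
- Spurious ORR difference = s × (ORR good − ORR poor).

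With ORR 20% and 8% by prognosis and s = 20%:

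- Favoured dose: 0.6 × 20% + 0.4 × 8% = 15.2%.
- Other dose: 0.4 × 20% + 0.6 × 8% = 12.8%.
- Difference: 0.20 × 12 = 2.4 points.

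The chance of at least 3 responders in 20, from the binomial distribution:

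| Share steered | Apparent ORR | P(at least 3/20) |
|---|---|---|
| 0% | 14.0% vs 14.0% | 54.5% vs 54.5% |
| 20% | 15.2% vs 12.8% | 60.5% vs 48.1% |
| 50% | 17.0% vs 11.0% | 68.5% vs 38.0% |

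**4. Range.** For prognostic gaps from 5 points (15% vs 10%) to 20 points (25% vs 5%), the spurious difference is 1.0 to 4.0 points at s = 20% and 2.5 to 10.0 points at s = 50%.

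**The case against.** The case for leaving the text alone has real substance.

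- **No comparison is claimed.** Section 10.1.5 judges each dose separately against 5.5%. Table 10.3.1-1 plans between-arm differences for Part 2A only. Section 10.3.9 makes interim analyses descriptive, and Section 3.2.1 says no prospective hypotheses are formally evaluated. This stands. A reader might infer that alternation decides which dose wins, but both doses may go to 40 (80 = 40 × 2), so expanding one does not displace the other. The harm is confined to informal reading of the doses side by side and to each dose's own chance of a signal.
- **Prediction needs conditions.** Assignment is central and follows confirmation of eligibility, and screening can last 28 days. A site must know the last study-wide assignment, know which doses have openings, and enrol before any other site. A reader might infer that every site always knows the next dose; the documents do not support that. Sponsor staff are better placed, although Section 7.5 gives data analysis and bioanalysis as the reasons for access, and the prioritisation clause is not tied to a dose.
- **The effect may be small.** A reader might reach a 6-point shift by supposing that 4 of 20 participants per dose are steered with a 15-point gap: 0.20 × 15 = 3 points per arm, in opposite directions. That is a ceiling. It needs every steered participant to displace one of the other prognosis in both arms. Under the model above the same inputs give 0.20 × 15 = 3 points in total, or 0.6 of a responder in 20. The sampling standard error of a 20-versus-20 difference at 15% is √(2 × 0.15 × 0.85/20), about 11 points. This answers the size of the concern but not the remedy: the planned intervals describe sampling error and do not allow for selection.
- **It may never arise.** With a single Part 2C dose there is nothing to alternate. However, the study schematic shows two groups of 20, and Section 5.2 provides for two.

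**Conclusion.** The point holds in a limited form. If more than one Part 2C dose is open, allocation is deterministic, and selection between doses is possible in an open-label cohort with investigator-reported response. The documents do not show that selection occurs. If a fifth of slots were steered, the spurious ORR difference would be about 1 to 4 points across the prognostic gaps assumed. In the central illustration, the chance of the 3-of-20 signal would be 60.5% against 48.1% for two equal doses. These figures rest on assumed prognostic mix, response rates and steering.

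A reader might also infer that the per-dose power statement is undermined. It is not: it reproduces at 80.6% and concerns one dose against a fixed rate. Nor do the documents show that Part 2B uses permuted blocks; they say only that its randomisation is even. The change is still worth making, because it removes a known weakness without adding participants and follows what Parts 2A and 2B already do.

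**What to change.** In Section 7.4, replace alternation with 1:1 randomisation through the IRT whenever two or more Part 2C doses are open, with the next assignment concealed from sites and from sponsor staff involved in enrolment. Use simple randomisation or varying block sizes; small fixed blocks remain fairly guessable. Stratifying by prior anti-PD-1/PD-L1 benefit is optional.

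Keep the fallback for a full dose. Flag participants assigned while only one dose was open, so that the randomised subset can be shown separately.

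Correct the wording that sends consecutive participants to different parts where dose levels must be meant. Reconcile Section 7.5, which calls Part 2 randomised, with Section 5.2, which lists Parts 2C and 2D as treated.

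Cost: an IRT reconfiguration, whose expense the documents do not give, and possibly slight imbalance between doses. The numbers stay at 20, then up to 40, per dose, and per-dose power is unchanged.
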